9. ENROLLMENT, REGISTRATION, AND RANDOMIZATION

9.1. Screening and Registration

Subjects (or their legally authorized representative [e.g., parent or legal guardian], where applicable) must provide informed consent before any screening tests are performed (see Section 17.3). When a subject signs the ICF, that subject is considered to be enrolled in the study. Participating study sites are required to document all screened candidates initially considered for inclusion in this study. If a subject is excluded from the study, the reasons for exclusion will be documented in the subject's source documents and on the screening log.

For subjects entering Part A, screening tender and swollen joint counts will be performed by an independent joint assessor at each site prior to study entry.

For subjects entering Part B, screening CLASI scores will be verified by an independent CLASI Adjudicator (Section 19.2.2) prior to study entry.

Subjects will be registered at the Screening Visit; as part of study screening, potential subjects will have the study risks and benefits explained to them, the associated ICF reviewed with them, and all their questions answered.

If a subject initially fails any of the screening criteria and is deemed as a screen failure by the end of the initial 28-day screening period, they will be allowed to be rescreened one time at the discretion of the Investigator. Upon rescreening, and in consultation with the Medical Monitor, subjects should repeat the Screening assessments and receive a new Screening Number.

9.2. Randomization of Subjects

Subjects will be randomized at the Day 1 Visit only after all screening assessments have been completed and the Investigator has verified that the subjects are eligible per criteria in Section 8. In addition, subjects will only be randomized after review of the narrative of SLE and CLE disease history, including relevant medical history that encompasses past infection, histological confirmation of CLE diagnosis (Part B) and receipt of the approval from the Medical Monitor. Randomization will be stratified by randomization factors (Section 7.1).

No subject may begin treatment prior to assignment of a unique identification number (registration) and randomization through the interactive response technology (IRT) system. Any subject identification numbers or randomization schedule assignments that have been assigned will not be reused even if the subject does not receive treatment. Rescreened subjects will be assigned a new number.

Subjects who withdraw from the study after randomization may not be replaced.

Refer to the Study Reference Guide for details on registration and randomization.

9.3. Blinding Procedures

This is a randomized, double-blind, placebo-controlled study.

CONFIDENTIAL

The information contained herein may not be used, disclosed, or published without the written consent of Biogen MA Inc.

All study staff will be blinded to the subject treatment assignments. To maintain the study blind, it is imperative that subject treatment assignments are not shared with the subjects, their families, or any member of the study team, either at the study site or at Biogen, except the unblinded Pharmacist (or designee) and the unblinded Pharmacy Monitor.

Efforts will be made to ensure that no members of the team involved in study conduct will be unblinded. Unblinding is permitted only in the case of a medical emergency or serious medical condition, when knowledge of the study treatment is essential for the immediate clinical management or welfare of the study subject, as judged by the Investigator.

Refer to the Study Reference Guide for details about unblinding.

There will be two IAs in the study.

For IA 1, a team of Biogen personnel independent of the study team will be set up to conduct the unblinded analysis for futility, as discussed in Section [16.7.1](#).

For IA 2, members of the Biogen study team not in direct contact with the study sites will have access to the study data after all subjects complete all Week 24 assessments in Part A and all Week 16 assessments in Part B. Members of the Biogen study team who become unblinded to the data for the IA at the end of the treatment periods, as described in Section [16.7.2](#), will have no further contact with study sites until after the final database lock.

All Investigators, study site personnel, and subjects will remain blinded to treatment assignments until after the final database lock.

CONFIDENTIAL

The information contained herein may not be used, disclosed, or published without the written consent of Biogen MA Inc.

10. DISCONTINUATION OF STUDY TREATMENT AND/OR WITHDRAWAL OF SUBJECTS FROM THE STUDY

10.1. Discontinuation of Study Treatment

A subject *must* permanently discontinue study treatment for any of the following reasons:

- The subject becomes pregnant. Study treatment must be discontinued immediately. Report the pregnancy according to the instructions in Section [15.4.1](#).
- The subject withdraws consent to continue study treatment.
- The subject experiences a medical emergency that necessitates permanent discontinuation of study treatment.
- The subject experiences a medical emergency that necessitates unblinding of the subject's treatment assignment.
- The subject is unwilling or unable to comply with the protocol.
- At the discretion of the Investigator for medical reasons.

The reason for discontinuation of study treatment must be recorded in the subject's electronic case report form (eCRF).

Subjects who prematurely **discontinue study treatment** during the Double-blind Treatment Period should complete all study assessments for the ET Visit as soon as possible, but within 4 weeks. Subjects who discontinue study treatment should also complete the study assessments for the Safety FU Visits at 4, 8, and 12 weeks after the ET Visit.

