RNA=ribonucleic acid; [REDACTED]; SLE=systemic lupus erythematosus; SLEDAI-2K=Systemic Lupus Erythematosus Disease Activity Index 2000; TB=tuberculosis; VAS=visual analog scale.

¹ Follow-up visit will be conducted 4, 8, and 12 weeks after the last Treatment Period Visit (Week 24 or ET).

² Assessments (e.g., CPK, ECG, etc.) may be performed as required to confirm SLEDAI-2K and BILAG findings.

³ On each dosing day (Day 1, Day 15, Day 29, Day 57, Day 85, Day 113, and Day 141) all assessments should be performed prior to dosing.

⁴ To be performed locally.

⁵ Where mandated by local regulation, a chest x-ray will be obtained locally during the screening period, unless a previous chest x-ray or the documented results from a chest x-ray obtained within 12 weeks prior to screening are available. The chest x-ray or x-ray results will be reviewed by the Investigator (or designee) in order to exclude patients with active TB infection from entering the study.

⁶ Testing to be performed locally. Indeterminate Quantiferon or T-SPOT tests may be repeated once and will be considered positive if retest results are positive or indeterminate. Subjects with documented BCG vaccination must perform a TB test at Screening and will be excluded if they exhibit skin induration ≥ 5 mm or a positive Quantiferon or positive or borderline T-SPOT (Elispot) test.

⁷ To be performed locally.

⁸ Height should be measured only once; i.e., at the Day 1/baseline visit.

⁹ Vital signs include seated arterial blood pressure, heart rate, and oral body temperature.

¹¹ One lesion is to be selected at baseline as the target lesion (the most severe active CLE lesion is recommended). The target lesion must be the same lesion used for tape harvesting and the same lesion over time.

¹² If the ET Visit occurs before Week 16, skin photography should be performed at the ET Visit.

¹³ Following administration of study treatment, subjects should remain at the study center for 1 hour to be observed for the development of potential allergic or anaphylactic reactions.

¹⁴ Subject paper diaries for recording corticosteroid use will be distributed on Day 1, reviewed with site staff at each study visit, and collected by the study site at the final study visit.

¹⁵ Only for subjects with prior B cell directed therapies within 52 weeks of Screening; this test should be performed at a central laboratory.

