Urinalysis (including microscopic examination)	X	X		X	X	X	X	X	X		X
Urine Protein-Creatinine Ratio (spot urine)	X	X		X	X	X	X	X	X		X
CD19+ B Cell Counts ¹⁶	X										
Pharmacokinetics											
Serum BIIB059 ¹⁷			X	X		X		X	X	X	X

CONFIDENTIAL

The information contained herein may not be used, disclosed, or published without the written consent of Biogen MA Inc.

CONFIDENTIAL

The information contained herein may not be used, disclosed, or published without the written consent of Biogen MA Inc.

	Screening Period	Treatment Period							Follow-up Period ¹			
		0	1	2	4	8	12	16/ ET	FU4	FU8	FU12	
Study Week	Within 4 Weeks Prior to Randomization	1 ³	8 (±2D)	15 ³ (±2D)	29 ³ (±3D)	57 ³ (±3D)	85 ³ (±3D)	113 (±3D)	141 (±5D)	169 (±5D)	197 (±5D)	
Tests and Assessments ^{2,3}												
Concomitant Medication/Procedures	Monitor and record from signing of informed consent through the end of the study											
Serious Adverse Events	Monitor and record from signing of informed consent through the end of the study											
Adverse Events			Monitor and record from time of first dose through the end of the study									

Abbreviations: ACR=American College of Rheumatology; C = complement; CLASI = Cutaneous Lupus Disease Area and Severity Index; CLE = cutaneous lupus erythematosus; CRP = C-reactive protein; D = day; DNA = deoxyribonucleic acid; dsDNA = double-stranded DNA; ECG = electrocardiogram; ESR = erythrocyte sedimentation rate; ET = early termination; FU = follow-up; HIV = human immunodeficiency virus; Ig = immunoglobulin; [REDACTED]; RNA = ribonucleic acid; [REDACTED]; SLE = systemic lupus erythematosus; SLEDAI-2K = Systemic Lupus Erythematosus Disease Activity Index; TB = tuberculosis; VAS = visual analog scale.

¹ Follow-up visits will be conducted 4, 8, and 12 weeks after the last Treatment Period Visit (Week 16 or ET).

² Assessments (e.g., CPK, ECG, etc.) may be performed as required to confirm SLEDAI-2K findings.

³ On each dosing day (Day 1, Day 15, Day 29, Day 57, and Day 85) all assessments should be performed prior to dosing.

⁴ To be performed locally.

⁵ Where mandated by local regulation, a chest x-ray will be obtained locally during the screening period, unless a previous chest x-ray or the documented results from a chest x-ray obtained within 12 weeks prior to screening are available. The chest x-ray or x-ray results will be reviewed by the Investigator (or designee) in order to exclude patients with active TB infection from entering the study.

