7.2.2. Treatment

Subject eligibility will be reconfirmed prior to randomization on Day 1. Eligible subjects will receive study treatment on Day 1 and return to the study site for additional dosing every 4 weeks through Week 20, with an additional dose at Week 2. Following each administration of study treatment, subjects should remain at the study center for 1 hour to be monitored for the development of potential allergic or anaphylactic reactions. Subjects will receive study treatment at baseline (Day 1), Week 2 (Day 15), Week 4 (Day 29), Week 8 (Day 57), Week 12 (Day 85), Week 16 (Day 113), and Week 20 (Day 141) for a total of 7 doses.

Subjects will undergo study assessments (see [Table 1](#)) at each of the dosing visits and will also undergo assessments at Week 1 (Day 8) and Week 24 (Day 169), though study treatment is not administered at these visits. The last dose of study treatment will be administered at Week 20 (Day 141).

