7.2.3. Follow-Up

Subjects are to return to the study site for follow-up (FU) visits at 4, 8, and 12 weeks after the last Treatment Period visit (Week 24 or Early Termination [ET] Visit). Follow-up visits will be conducted at Week FU4 (Day 197), Week FU8 (Day 225) and Week FU12 (Day 253). The final study visit will be Week FU12.

Subjects who prematurely **discontinue study treatment** during the Double-blind Treatment Period should complete all study assessments for the Week 24/ET Visit as soon as possible, but within 4 weeks. Subjects who discontinue study treatment should also complete the study assessments for the Safety FU Visits at Week FU4, Week FU8, and Week FU12 after their ET Visit.

Subjects who are prematurely **withdrawn from the study** during the Double-blind Treatment Period should complete all study assessments for the Week 24/ET Visit as soon as possible, but within 4 weeks. Withdrawn subjects should also be encouraged to complete the study assessments for the Safety FU Visits at Week FU4, Week FU8, and Week FU12, after their ET Visit. However, if the subject is unwilling or unable to attend the study FU Visits, or at minimum the ET Visit, and decides to withdraw consent, the reason for withdrawal will be documented and no further assessments will be obtained.

CONFIDENTIAL

The information contained herein may not be used, disclosed, or published without the written consent of Biogen MA Inc.

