7.3.3. Follow-Up

Subjects are to return to the study site for follow-up visits on Week FU4 (Day 141), Week FU8 (Day 169), and Week FU12 (Day 197) after the last Treatment Period visit (Week 16 or ET Visit). The final study visit will be Week FU12.

Subjects who prematurely **discontinue study treatment** during the Double-blind Treatment Period should complete all study assessments for the Week 16/ET Visit as soon as possible, but within 4 weeks. Subjects who discontinue study treatment should also complete the study assessments for the Safety FU Visits at Week FU4, Week FU8, and Week FU12 after their ET Visit.

Subjects who are prematurely **withdrawn from the study** during the Double-blind Treatment Period should complete all study assessments for the Week 16/ET Visit as soon as possible, but within 4 weeks. Withdrawn subjects should be encouraged to complete the study assessments for the Safety FU Visits at Week FU4, Week FU8, and Week FU12 after their ET Visit.

CONFIDENTIAL

The information contained herein may not be used, disclosed, or published without the written consent of Biogen MA Inc.

However, if the subject is unwilling or unable to attend the study FU Visits, or at minimum the ET Visit, and decides to withdraw consent, the reason for withdrawal will be documented and no further assessments will be obtained.

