10.2. Withdrawal of Subjects From Study

Subjects must be withdrawn from the study for any one of the following reasons:

- The subject withdraws consent.
- The subject enrolls into another interventional clinical study in which an investigational treatment or approved therapy for investigational use is administered.
- The subject is unwilling or unable to comply with the protocol.

Subjects who are prematurely **withdrawn from the study** during the Double-blind Treatment Period should complete all study assessments for the ET Visit as soon as possible, but within 4 weeks. Withdrawn subjects should be encouraged to complete the study assessments for the Safety FU Visits at 4, 8, and 12 weeks after the ET Visit. However, if the subject is unwilling or unable to attend the study FU Visits, or at minimum the ET Visit, and decides to withdraw consent, the reason for withdrawal will be documented and no further assessments will be obtained.

The reason for the subject's withdrawal from the study must be recorded in the subject's eCRF. The level of consent withdrawal (e.g., whether samples collected but not yet analyzed can still be used/analyzed, and so on) should also be recorded in the eCRF.

CONFIDENTIAL

The information contained herein may not be used, disclosed, or published without the written consent of Biogen MA Inc.

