11.2. Study Treatment Precautions

Following administration of study treatment, subjects should remain at the study center for 1 hour to monitor for the development of potential allergic or anaphylactic reactions.

Epinephrine for SC injection, diphenhydramine (or equivalent) for IV injection, and any other medications and resuscitation equipment for the emergency management of anaphylactic reactions must be available in the room where the infusion is being performed.

BIIB059 or placebo should be administered within the stated window of the scheduled visit (± 2 or 3 days; see [Table 1](#) and [Table 2](#)). If a subject misses a planned dose (i.e., outside of the 2- or 3-day window), the missed dose should be administered as soon as possible, and no later than 5 days after the last day of the planned window. If the Week 2 dose (the second dose to be

CONFIDENTIAL

The information contained herein may not be used, disclosed, or published without the written consent of Biogen MA Inc.

administered in the study) can't be given within the planned window, the missed dose should be skipped and the subject should receive the next scheduled dose as per protocol.

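### For early discontinuers the final follow-up visit is timed from ET and not from the last dose, so it can nominally fall up to 28 days before the 16-week post-dose restrictions end

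*Protocol*

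**What the plan says.** Follow-up after early discontinuation is counted from the ET visit throughout the protocol:

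- Section 10.1: subjects who discontinue treatment "should also complete the study assessments for the Safety FU Visits at 4, 8, and 12 weeks after the ET Visit".
- Section 10.2: subjects withdrawn from the study "should be encouraged to complete the study assessments for the Safety FU Visits at 4, 8, and 12 weeks after the ET Visit".
- Sections 7.2.3 and 7.3.3, and footnote 1 of Tables 1 and 2, use the same anchor: the last Treatment Period visit, which is Week 24 (Part A) or Week 16 (Part B), or ET.

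ET itself is due promptly, and at most four weeks later. No minimum time from the last dose is given.

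The restrictions on subjects use a different anchor. Contraception (8.1.1, 15.5), pregnancy avoidance (15.4.1) and the live-vaccine ban (11.4.1.1.5) all run to 16 weeks after the last dose.

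Urine pregnancy tests are scheduled at FU4, FU8 and FU12 in both parts (Tables 1 and 2). Under 15.3.1 adverse events are recorded up to the final follow-up visit. Under 15.3.3, SAEs after that visit are reported only if judged related. Section 11.2 allows a missed dose, other than the Week 2 dose, to be given "no later than 5 days after the last day of the planned window".

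**The concern.** For a completer, the final visit falls nominally on the last day of the 16-week window. That match depends on the 28 days between the last planned dose and the Week 24 or Week 16 visit. When ET replaces that visit the interval can be shorter, and the more promptly ET is done, the earlier the last visit falls relative to the last dose. Some stops can come soon after a dose, for example the mandatory stop for a medical emergency in 10.1.

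Such a subject is under the same 16-week restrictions as a completer, but the last scheduled pregnancy test and safety visit can precede their end. A pregnancy beginning late in the window would then come to light through the subject or the Investigator's general duty to monitor pregnancies (15.6.1), and not through a planned test.

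**Working it through.** **Inputs**

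- Restriction length: 16 weeks = 112 days after the last dose (15.4.1, 15.5, 11.4.1.1.5).
- Dosing days: 1, 15, 29, 57 and 85 in both parts, plus 113 and 141 in Part A (7.2.2, 7.3.2).
- Final visit: 12 weeks = 84 days after ET. For completers, Day 253 in Part A and Day 197 in Part B (7.2.3, 7.3.3).
- Windows (Tables 1 and 2): ±2 days at Week 2, ±3 days from Week 4 to the end of treatment, ±5 days at follow-up visits. Late dose: 5 days beyond the window (11.2).

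**Step 1. Completers, nominal**

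Part A: 253 − 141 = 112 days. Part B: 197 − 85 = 112 days. The shortfall is 0 in both parts.

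**Step 2. Early discontinuers, nominal**

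With ET d days after the last dose, the final visit is 84 + d days after that dose. The shortfall is 112 − (84 + d) = 28 − d, or zero once d reaches 28.

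| Case | Last dose | ET | d | Final visit after last dose | Shortfall |
|---|---|---|---|---|---|
| ET on the day of the last dose | – | – | 0 | 84 | 28 |
| ET at the Week 1 visit | Day 1 | Day 8 | 7 | 91 | 21 |
| Pre-dose stop at Week 2 | Day 1 | Day 15 | 14 | 98 | 14 |
| Pre-dose stop at Week 4 | Day 15 | Day 29 | 14 | 98 | 14 |
| Pre-dose stop at Week 8 | Day 29 | Day 57 | 28 | 112 | 0 |

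Later dosing visits are also 28 days apart, so a pre-dose stop at any of them is nominally not short.

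**Step 3. Early discontinuers, with allowed windows**

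- Week 2 stop: ET on Day 13 to 17, so d = 12 to 16 and the shortfall is 12 to 16 days. With the final visit moved by ±5 days it is 7 to 21.
- Week 4 stop: d runs from 26 − 17 = 9 to 32 − 13 = 19, so the shortfall is 9 to 19 days. With ±5 days it is 4 to 24.
- Maximum: d = 0 and the final visit 5 days early gives 84 − 5 = 79 days, and 112 − 79 = 33 days short.

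**Step 4. Completers, with allowed windows**

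- FU12 on its fixed study day. Part A: latest dose 141 + 3 + 5 = Day 149, earliest FU12 253 − 5 = Day 248, and 248 − 149 = 99 days. Part B: latest dose 85 + 3 + 5 = Day 93, earliest FU12 197 − 5 = Day 192, and 192 − 93 = 99 days. Both are 112 − 99 = 13 days short.
- FU12 counted from an early last treatment visit, as footnote 1 permits. Part A: Week 24 on Day 166, FU12 on 166 + 84 − 5 = Day 245, and 245 − 149 = 96 days. Part B: Week 16 on Day 110, FU12 on 110 + 84 − 5 = Day 189, and 189 − 93 = 96 days. Both are 112 − 96 = 16 days short.

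**The case against.** The strongest reply is that nothing is broken. The 16-week limits bind the subject, and no section promises visits or tests until they expire. Follow-up is defined as 12 weeks after the last treatment visit or ET, 11.4.1.4 describes it as about five half-lives, and early discontinuers get it in full. The 112 days for completers follows from the visit grid and is not a stated requirement. All of this stands.

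Much of the safety net also continues. Pregnancies are reportable within 24 hours of site awareness, with no cut-off at the final visit (15.4.1). Related SAEs remain reportable, and ongoing SAEs are followed to resolution or stability (15.3.2, 15.3.3). The adverse event rows of Tables 1 and 2 run to the end of the study, which 7.5 defines as the last subject's last visit, so whether routine capture stops at the subject's own final visit is partly ambiguous. No FU12 procedure is specific to live vaccines. This stands too, and it limits the point to scheduled observation.

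Completers can also finish short through allowed windows, by 13 or 16 days, which is about the size of the 14-day case. That is correct. It makes the difference between the groups one of degree, though the early discontinuer's maximum of 33 days is still larger.

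Finally, simply delaying the last visit would leave a long untested stretch. With FU8 kept at 56 days after ET, the gap to the final visit would be 112 − (d + 56) = 56 − d days: 42 at d = 14 and 56 at d = 0. This is a real drawback, and spacing the visits evenly answers it.

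**Conclusion.** The point holds as a small, optional improvement. For early discontinuers who attend follow-up, the last scheduled pregnancy test and routine safety visit come nominally 28 − d days before the protocol's own restrictions end when d is below 28.

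The 14-day figure assumes that ET is done at the Week 2 or Week 4 visit itself. Each day of delay in ET takes a day off the shortfall. The 28-day figure needs ET on a dosing day. How many subjects would be affected is not known, and the documents do not say that stops cluster early.

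A reader might infer that the protocol contradicts itself, that early discontinuers are left without pregnancy or safety surveillance, or that 12 weeks is pharmacologically too short. The documents support none of these. The restrictions and the reporting duties continue, and nothing in the documents shows that about five half-lives of follow-up is inadequate. No efficacy result changes: SAP 6.6.1 already treats data after treatment discontinuation as missing in the primary analysis.

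**What to change.** In 7.2.3, 7.3.3, 10.1, 10.2 and footnote 1 of Tables 1 and 2, set the final follow-up visit for early discontinuers at the later of 12 weeks after ET and 16 weeks after the last dose. Keep its urine pregnancy test, adverse event collection and 5-day window. When the second date applies, space the three existing follow-up visits about evenly between ET and that date, at intervals of (112 − d)/3 days:

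- d = 14: 98/3, about 33 days.
- d = 0: 112/3, about 37 days.

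This removes the nominal shortfall for every stop time, and no interval between tests reaches 6 to 8 weeks.

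The cost is amendment wording and no added visit. For some early discontinuers the final visit is up to 4 weeks later, and in the two cases above the interval between visits is about 5 to 9 days longer than the present 28. The last subject's last visit could be slightly later. Subjects who withdraw consent and do not attend are not covered, an actual visit could still be 5 days short through its window, and the window variation for completers is left as it is.
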